##### **12.4.4.1 Continuous Endpoints**

The actual results and the change from baseline values at each post-baseline visit will be summarised by treatment group using descriptive statistics.

The mean change from baseline values ( $\pm$ SD) over time will also be presented graphically.

The change from baseline values will be compared between the FT011 and placebo groups using a mixed model repeated measures model with the baseline value a covariate, treatment group as fixed effect, the interaction effect between study visit and treatment group, and subject as random effect with an unstructured covariance assumption. Parameter estimates will be calculated using restricted maximum likelihood methods, and the Kenward-Rogers method will be used to calculate the degrees of freedom.

The least squares means, estimated treatment differences (compared to placebo) and the corresponding confidence intervals and p-values at each visit will be presented.

The numeric CRIS scores be analysed using a Wilcoxon test.

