##### **12.4.4.2 Binary Endpoints**

Binary endpoints will be summarised using counts, percentages, and odds ratios (compared to placebo). The proportions between each FT011 group and the placebo group will be compared using a Cochran-Mantel-Haenszel test.

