2.2. SECONDARY OBJECTIVES AND ENDPOINTS

The secondary objectives are:

- To assess the safety and tolerability of oral FT011 compared to placebo in participants with diffuse SSc.
- To evaluate the short-term efficacy of oral FT011 compared to placebo in improving disease activity in participants with diffuse SSc.

Document: \$506df00529e1\$BDE32479744D47F0B3BAA4285D5BE091.docx

Author: ██████████

Version Number: Final v1.1

Version Date: 16Nov2022

Template No.: CS_TP_BS016 Revision 6

Reference: CS_WI_BS005

Effective Date: 02Dec2019

Copyright © 2009, 2010, 2012, 2016, 2018, 2019 IQVIA. All rights reserved. The contents of this document are confidential and proprietary to IQVIA Holdings Inc. and its subsidiaries. Unauthorized use, disclosure or reproduction is strictly prohibited.

The secondary endpoints are:

- Safety will be assessed by:
 - o Treatment-emergent adverse events from first dose of study drug to End of Study.
 - o Physical examination.
 - o Vital signs (blood pressure, heart rate, respiratory rate, and temperature).
 - o 12-lead electrocardiograms (ECG).
 - o Safety laboratory results (haematology, biochemistry, coagulation, and urinalysis).
 - o Use of concomitant medications.
- Efficacy will be assessed by:
 - o Change in modified Rodnan skin score (mRSS) from Baseline at each visit.
 - o Change in percent predicted forced vital capacity (FVC) from Baseline to Week 4, Week 8, and Week 12.
 - o Change in Scleroderma Health Assessment Questionnaire - Disability Index (SHAQ-DI) Score from Baseline to Week 4, Week 8, and Week 12.
 - o Change in Patient Global Assessment Score from Baseline to Week 4, Week 8, and Week 12.
 - o Change in Physician Global Assessment Score from Baseline to Week 4, Week 8, and Week 12.
 - o The proportion of patients showing an improvement (defined as ACR Composite Response Index in Diffuse Cutaneous Systemic Sclerosis (CRISS) score predicted probability of ≥ 0.60) at Week 12.
 - o Change in the Scleroderma Clinical Trials Consortium Damage Index (SCTC-DI) score from Baseline to Week 12.
 - o Change in the 5-D Itch Scale from Baseline to Week 12.

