14.2.1.10 ANALYSIS OF EFFICACY VARIABLES

The observed values and change from baseline values for mRSS, percent predicted FVC, HAQ-DI, patient global assessment score, and physician global assessment score, and SCTC-DI score will be listed for each participant at each protocol specified visit and will be summarised using descriptive statistics over time by treatment group and for all participants.

Actual and change from baseline values will be presented graphically by treatment group using a jitter plot and overlaid box-whisker plot (median, 25th and 75th percentiles) over time.

For mRSS, HAQ-DI, SCTC-DI and 5-D Itch Scale the individual item responses will also be summarised and listed for each participant.

The 5-D itch scale at baseline and at Week 12 will be listed for each participant and will be summarised using descriptive statistics. The change from baseline to Week 12 will also be summarised.

Even though no formal hypothesis testing is planned for this study, exploratory analyses may be performed to assess the treatment effect of FT011 on the efficacy outcomes if data indicates trend and model assumptions hold.

For mRSS, percent predicted FVC, HAQ-DI, patient global assessment score, and physician global assessment score, the change from baseline values will be compared between the FT011 and placebo groups using a mixed model for repeated measures with the baseline value as a covariate, treatment group as fixed effect, the interaction effect between study visit and treatment group, and participant as random effect using an unstructured covariance structure. Parameter estimates will be calculated using restricted maximum likelihood methods (REML), and the Kenward-Rogers method for determining the degrees of freedom. This method will assume that any missing data is Missing at Random (MAR). Example SAS code for the mixed model (using SAS Proc Mixed) is:

Document: \$506df00529e1\$BDE32479744D47F0B3BAA4285D5BE091.docx

Author: ████████████████████

Version Number: Final v1.1

Version Date: 16Nov2022

Template No.: CS_TP_BS016 Revision 6

Reference: CS_WI_BS005

Effective Date: 02Dec2019

```
PROC MIXED data=libname.ADXX REML;  
CLASS TRT01P VISIT SUBJID;  
MODEL AVAL = TRT01P|VISIT BASELINE / DDFM = KENWARDROGER;  
RANDOM VISIT / SUBJECT = SUBJID TYPE = UN;  
LSMEANS TRT01P|VISIT / PDIFF = CONTROL('PLACEBO') CL ;  
RUN;
```

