Details of model including covariance structure will be decided based on the model fit. The least squares means, estimated treatment differences (compared to placebo) with two-sided 95% confidence intervals and p-values will be presented.

The CRISS score and SCTC-DI score will be compared between FT011 and placebo group using a Wilcoxon rank-sum test at each post-baseline visit. Example SAS code for this is:

```
PROC NPAR1WAY DATA=LIBNAME.ADXX (where=(trt01p in (placebo treatment_groupX)) WILCOXON;  
CLASS TRT01P;  
VAR AVAL;  
EXACT WILCOXON;  
RUN;
```

The proportions (binary outcomes) of participants showing an:

- improvement in CRISS at Week 12

will be listed, summarised and compared using the Cochran-Mantel-Haenszel test. Example SAS code for the Cochran-Mantel-Haenszel test in SAS Proc Freq is:

```
PROC FREQ DATA=LIBNAME.ADXX;  
TABLES TRT01P*AVAL / CMH;  
RUN;
```

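### SAP 14.2.1.10 does not say that the SCTC-DI test uses change from baseline, and its CMH example code pools three arms where the protocol compares each dose with placebo; SAP 3.3 lists neither departure

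*SAP*

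**What the plan says.** **SCTC-DI.** SAP 2.2 gives the endpoint as "Change in the Scleroderma Clinical Trials Consortium Damage Index (SCTC-DI) score from Baseline to Week 12", and Protocol 7.2.2 agrees. For continuous endpoints Protocol 12.4.4.1 says: "The change from baseline values will be compared between the FT011 and placebo groups using a mixed model repeated measures model", with baseline as a covariate. It gives the rank test to one variable only: "The numeric CRIS scores be analysed using a Wilcoxon test". SAP 14.2.1.10 keeps the mixed model for mRSS, percent predicted FVC, HAQ-DI and the two global assessments, and says of these that "the change from baseline values will be compared between the FT011 and placebo groups using a mixed model for repeated measures". SCTC-DI is not in that list. Instead: "The CRISS score and SCTC-DI score will be compared between FT011 and placebo group using a Wilcoxon rank-sum test at each post-baseline visit".

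**CRISS improvement at Week 12.** Protocol 12.4.4.2 says: "The proportions between each FT011 group and the placebo group will be compared using a Cochran-Mantel-Haenszel test". It also asks for odds ratios against placebo. The SAP says only that the proportions are listed, summarised and compared by a CMH test. Its example code reads the whole dataset and requests "TABLES TRT01P*AVAL / CMH".

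**Status.** Protocol section 12 gives the SAP precedence over the protocol. SAP 3.3 declares two changes: an added screened set and the inversion of the patient global score. SAP 14.2 calls the efficacy comparisons exploratory.

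**The concern.** Two secondary efficacy analyses could be programmed, in line with the SAP, as something other than the stated endpoint or contrast.

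For SCTC-DI, a test of the raw Week 12 score is valid on average because of randomisation. With about 10 participants per arm, though, it carries any chance imbalance at baseline, and it loses precision if the score is stable over 12 weeks.

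For CRISS improvement, a three-arm test cannot show which dose differs from placebo and yields no odds ratio per dose. If the one-degree-of-freedom correlation statistic were reported, its value would depend on the order in which the arms are sorted.

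Because the SAP prevails and SAP 3.3 is silent, a reader of the results would not know that the protocol's analysis had been replaced.

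**Working it through.** Neither document gives a figure to reproduce: the sample size of 30 (10 per arm) is practical, with no effect size or SD. The check is a comparison of texts, then an illustration of size under stated assumptions.

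**1. SCTC-DI: which variable is tested?**

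- The CRISS score is computed from changes (SAP 14.2.1.6), so it needs no qualifier. SCTC-DI is a level on a 0–55 scale (SAP 14.2.1.7), so it does.
- SAP 14.2.1.10 elsewhere separates observed values from changes, so leaving the word out leaves a real choice open.
- The code does not settle it. `AVAL` is the Wilcoxon variable, but it is also the response in the mixed-model example, where change is meant.
- The reference to each post-baseline visit does not fit: Protocol Table 1 schedules SCTC-DI only on Day 1 and at Week 12.

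**2. SCTC-DI: size.** Assume equal variance at both visits and a baseline-to-Week 12 correlation r, which the documents do not give.

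- Var(change)/Var(raw) = 2(1 − r).
- SD of a baseline mean difference at 10 per arm = √(2/10) = 0.447 SD. P(|difference| > 0.5 SD) = 2[1 − Φ(0.5/0.447)] = 0.264.
- A baseline imbalance of 0.5 SD shifts the raw comparison by 0.5r and the change comparison by 0.5(r − 1).

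| r | Variance ratio | Shift, raw (SD) | Shift, change (SD) |
|---|---|---|---|
| 0.3 | 1.4 | 0.15 | −0.35 |
| 0.5 | 1.0 | 0.25 | −0.25 |
| 0.7 | 0.6 | 0.35 | −0.15 |
| 0.8 | 0.4 | 0.40 | −0.10 |
| 0.9 | 0.2 | 0.45 | −0.05 |

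A simulation (20,000 runs, normal data, 10 per arm, two-sided 5%, assumed true effect of 1 SD) gives power as follows. The baseline-adjusted column is analysis of covariance, standing in for the protocol's model at a single visit.

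| r | Wilcoxon, raw | Wilcoxon, change | Baseline-adjusted |
|---|---|---|---|
| 0.5 | 0.51 | 0.52 | 0.66 |
| 0.7 | 0.51 | 0.73 | 0.81 |
| 0.8 | 0.51 | 0.89 | 0.92 |
| 0.9 | 0.51 | 0.99 | 0.995 |

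Type I error was about 0.04 to 0.05 for all three.

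**3. CMH: which table is formed?** The Wilcoxon code just above is restricted to placebo and one treatment group. The CMH code has no such restriction, so with three arms it forms one 3×2 table.

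**4. CMH: size.** Assumed responders are 2/10 on placebo, 3/10 on 200 mg and 7/10 on 400 mg. With a single stratum, Q = (N − 1)/N × Pearson chi-square.

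- *Three arms, general association.* Expected responders are 4 per arm. Pearson = (4 + 1 + 9)(1/4 + 1/6) = 5.833. Q = 29/30 × 5.833 = 5.639 on 2 df, p = 0.060.
- *Three arms, correlation statistic (N − 1)r², where r is now the correlation of arm score with response.* Ordered placebo, 200 mg, 400 mg (SAP Appendix 1): 29 × 25/144 = 5.035, p = 0.025. Ordered alphabetically (200 mg, 400 mg, placebo): 29 × 1/144 = 0.201, p = 0.65.
- *200 mg v placebo.* Pearson = 0.5(1/2.5 + 1/7.5) = 0.267. Q = 19/20 × 0.267 = 0.253, p = 0.61. OR = (3 × 8)/(7 × 2) = 1.71, Wald 95% CI 0.22 to 13.4. Fisher exact p = 1.00.
- *400 mg v placebo.* Pearson = 12.5(1/4.5 + 1/5.5) = 5.051. Q = 19/20 × 5.051 = 4.798, p = 0.0285. OR = (7 × 8)/(3 × 2) = 9.33, Wald 95% CI 1.19 to 73.0. Fisher exact p = 0.070.

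With responders 1, 6 and 3, the three-arm test gives p = 0.064, against 0.022 for 200 mg and 0.28 for 400 mg.

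**The case against.** The strongest reply is that these are gaps in wording rather than demonstrated wrong analyses. SAP 2.2 defines the SCTC-DI endpoint as change, and 14.2.1.10 summarises its change. The code is labelled as an example, the neighbouring examples compare with placebo, and the output templates, which were not supplied, may restore per-dose results. Protocol 12.4.4 leaves inferential detail to the SAP, and a repeated-measures model suits an endpoint with one post-baseline assessment poorly. The responder counts are invented: with 2, 2 and 7 the overall test (p = 0.031) and the 400 mg contrast (p = 0.028) agree, and with 2, 4 and 6 both miss 0.05 (0.20 and 0.075). The comparisons are exploratory and will be run only if the data suggest a trend.

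Much of this stands as a limit on size. It is not shown that the raw SCTC-DI score will be tested, and a rank test at one visit is reasonable. The p-values show what can happen, not what will; by Fisher's exact test the 400 mg contrast in the main illustration is not below 0.05. The row-order effect arises only if the correlation statistic is the one reported.

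It does not remove the point. Nothing in the SAP's CMH text restores the comparison of each dose with placebo or the odds ratio, so the code is the only specification supplied. With one visit, the protocol's model reduces to a baseline-adjusted comparison of change, so moving SCTC-DI to an unadjusted rank test is a change of method that belongs in SAP 3.3.

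**Conclusion.** The concern holds, and the CMH part is the stronger. Followed as written, the code cannot deliver the per-dose comparison or odds ratio that the protocol promises; this follows from the shape of the table and needs no assumption. How far the p-values diverge depends on the responder counts.

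For SCTC-DI, the defect is that the analysed variable is not named and the literal reading departs from the endpoint. Its cost depends on an unknown correlation. At 0.7 to 0.9, plausible for a damage index over 12 weeks but assumed here, change has 0.6 to 0.2 times the variance of the raw score. Below 0.5 change is the less precise, and the case for it rests on the endpoint definition alone. These figures also assume equal variances, and the power figures assume normal data, which a bounded score may not follow.

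Both items should be corrected. They affect exploratory analyses of secondary endpoints, not the primary pharmacokinetic objective.

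**What to change.** - **SCTC-DI.** State in SAP 14.2.1.10 that the Wilcoxon test uses change from baseline to Week 12, at Week 12 only, and name the change variable in the code (`VAR CHG`). A baseline-adjusted comparison of change, closer to the protocol, is an acceptable alternative.
- **CMH.** Restrict the code to placebo plus one FT011 dose at a time, with the same `WHERE` clause as the Wilcoxon code. Report each odds ratio against placebo with its 95% confidence interval.
- **SAP 3.3.** Record the move of SCTC-DI from the mixed model to the Wilcoxon test. If a three-arm CMH test is intended, list that too, naming the statistic and the row order.

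The cost is about two lines of SAP text and code and an entry in section 3.3. No new data are needed.

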## 5 STUDY PLAN

### 5.1 Overall Trial Design

This is a multi-centre, randomised, double blind, placebo-controlled study to assess the PK and PD effects and safety of FT011 in participants with diffuse systemic sclerosis.

The targeted study population is patients with diffuse SSc with a disease duration of  $\leq 10$  years from onset of first non-Raynauds symptom, and a modified Rodnan Skin Score (mRSS) of 15 to 40 at the screening visit. Patients meeting all eligibility criteria will have a baseline skin biopsy (2 x 3mm punch biopsies) taken before being randomised 1:1:1 to FT011 200mg, FT011 400mg, or placebo.

Participants will take their investigational medicinal product (IMP) once a day for 3 months (12 weeks), in addition to their standard-of-care scleroderma medications. They will return to the site for study visits at Weeks 4, 8, and 12. Week 12 is the end of the study Treatment Period. A final study follow-up visit will be conducted one month after they complete treatment (Week 16).

Visit procedures will include skin thickness assessments using the mRSS at every visit, and forced vital capacity (FVC), the Scleroderma Health Assessment Questionnaire- Disability Index (SHAQ-DI), and physician and patient global assessments at each visit during the Treatment Period. A follow up skin biopsy will be taken at Week 12. On Day 1 and at Week 12 participants will have serial PK samples collected out to 8 hours post-dose, and trough samples will be collected at each interim visit. Other on-study visit assessments will include additional participant questionnaires, physical examinations, vital signs measurements, safety laboratory blood and urine tests, and electrocardiograms. Adverse events and concomitant medications will be assessed and recorded at each study visit. Additional blood samples will be collected at Day 1 and Week 12 for exploratory assessments.

[figure not shown]
With the exception of methotrexate, which is excluded, participants should be maintained on their current SSc medications during the course of the Treatment Period unless they meet the following progression criteria; those who have a mRSS increase from Baseline of 5 or more may start immunosuppressive medications, or, if already taking these, have their immunosuppressive medications or doses changed.

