3. STUDY DESIGN

3.1. GENERAL DESCRIPTION

This is a multi-centre, randomised, double blind, placebo-controlled study to assess the PK and PD effects and safety of FT011 in participants with diffuse SSc.

A total of approximately 30 participants, 10 per treatment group, will be randomised and treated. The sample size for this study is sized based on practical considerations and a formal sample size calculation was not performed.

The targeted study population is participants with diffuse SSc with a disease duration of ≤ 10 years from onset of first non-Raynauds symptom, and a modified Rodnan Skin Score (mRSS) of 15 to 40 at the screening visit. Participants meeting all eligibility criteria will have a baseline skin biopsy (2 x 3 mm punch biopsies) taken before being randomised 1:1:1 to FT011 200 mg, FT011 400 mg, or placebo.

Participants will take their study drug once a day for 3 months (12 weeks), in addition to their standard-of-care scleroderma medications. They will return to the site for study visits at Weeks 4, 8, and 12. Week 12 is the end of the study Treatment Period. A final study follow-up visit will be conducted one month after they complete treatment (Week 16).

Visit procedures will include skin thickness assessments using the mRSS at every visit, and forced vital capacity (FVC), the Scleroderma Health Assessment Questionnaire-Disability Index (SHAQ-DI), and Physician and Patient Global Assessments at all visits during the Treatment Period. A follow up skin biopsy will be taken at Week 12. On Day 1 and at Week 12 participants will have serial PK samples collected out to 8 hours post-dose, and trough samples will be collected at each interim visit. Other on-study visit assessments will include additional participant questionnaires, physical examinations, vital signs measurements, safety laboratory blood and urine tests, and electrocardiograms. Adverse events and concomitant medications will be assessed and recorded at each study visit.

Additional blood samples will be collected at Day 1 and Week 12 for exploratory assessments.

With the exception of methotrexate, which is excluded, participants should be maintained on their current SSc medications during the course of the Treatment Period unless they meet the following progression criteria; those who have a mRSS increase from Baseline of 5 or more may start immunosuppressive medications, or, if already taking these, have their immunosuppressive medications or doses changed.

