6.1. SUMMARY STATISTICS

For categorical variables, the population size (N for population group totals and n for available data for each treatment group) and the percentage (of available data) for each class of the variable will be presented. Continuous variables will be summarized using descriptive statistics, including number of participants (n), mean, standard deviation (SD), median, minimum, and maximum values. The coefficient of variation (CV%), geometric mean and geometric CV% will be presented for the PK tables.

95% Confidence Intervals will be reported where appropriate. If not mentioned otherwise, all statistical tests will be performed with a type I two-sided error rate of 5%.

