14.2. EFFICACY ANALYSIS

All efficacy analysis will be presented using the mITT Analysis set. The statistical comparisons described in this SAP for the efficacy variables are exploratory only, and no formal hypotheses testing will be undertaken.

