Version Number: Final v1.1

Version Date: 16Nov2022

Template No.: CS_TP_BS016 Revision 6

Reference: CS_WI_BS005

Effective Date: 02Dec2019

Participants for which the predicted probability is greater or equal to 0.60 are considered improved, while participants for which the predicted probability is below 0.60 are considered not improved.

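### For the CRISS score, CRISS response and SCTC-DI, the SAP specifies tests but no between-arm estimate with a confidence interval; the protocol's odds ratio for CRISS response is fragile at 10 per arm

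*SAP*

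**What the plan says.** Both documents treat efficacy as exploratory. SAP section 14.2 says that "no formal hypotheses testing will be undertaken". On size, SAP section 3.1 says: "A total of approximately 30 participants, 10 per treatment group, will be randomised and treated". It adds: "The sample size for this study is sized based on practical considerations and a formal sample size calculation was not performed".

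For the CRISS and SCTC-DI scores, SAP section 14.2.1.10 says: "The CRISS score and SCTC-DI score will be compared between FT011 and placebo group using a Wilcoxon rank-sum test at each post-baseline visit". Its example code requests the asymptotic and exact Wilcoxon tests and nothing else. Protocol section 12.4.4.1 also names only a Wilcoxon test for the CRISS score.

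For CRISS response, SAP section 14.2.1.6 sets the cut: "Participants for which the predicted probability is greater or equal to 0.60 are considered improved". Section 14.2.1.10 then plans a listing, a summary and a CMH test. Protocol section 12.4.4.2 goes further: "Binary endpoints will be summarised using counts, percentages, and odds ratios (compared to placebo".

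The SAP does not mention the odds ratio. Section 3.3 of the SAP lists two changes from the protocol, and dropping the odds ratio is not one of them. Protocol section 12 gives the SAP precedence on methods.

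**The concern.** A trial of about 30 participants with no power calculation and no formal testing has to be read from estimates and their uncertainty. For the composite efficacy endpoint, the SAP text specifies p-values. The protocol adds one effect measure, which cannot be computed when an arm has no responders or only responders. The five components of CRISS are each given a treatment difference with a 95% interval, so the composite is reported less informatively than its parts. A later trial planned on CRISS would need an effect size and its uncertainty, and this plan does not commit to either in a form that is sure to exist.

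**Working it through.** **1. Specified between-arm output, endpoint by endpoint.**

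| Endpoint | SAP 14.2.1.10 | Protocol 12.4.4 |
|---|---|---|
| mRSS, FVC, HAQ-DI, both globals | Mixed model: difference, 95% CI, p-value | Same |
| CRISS score | Wilcoxon test | Wilcoxon test |
| SCTC-DI | Wilcoxon test (plus per-arm descriptives) | Mixed model for continuous endpoints |
| CRISS response | CMH test (plus summary) | Counts, percentages, odds ratio, CMH test of each dose vs placebo |

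The SAP's Wilcoxon code restricts the data to placebo and one dose. Its CMH code has no such filter. As written it runs on a three-arm table, for which no single odds ratio is defined.

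**2. How often the odds ratio fails.** The documents give no power, effect size or response rate, so there is no planned figure to reproduce. Inputs are n = 10 per arm (SAP 3.1) and assumed response rates p0 (placebo) and p1 (FT011). The sample odds ratio is zero, infinite or undefined if either arm has 0 or 10 responders:

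P(fail) = 1 − [1 − (1−p0)^10 − p0^10] × [1 − (1−p1)^10 − p1^10]

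Example with p0 = 10% and p1 = 30%: 0.9^10 = 0.349 and 0.7^10 = 0.028, and the all-responder terms are negligible. So P = 1 − 0.651 × 0.972 = 0.367.

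| Placebo rate | FT011 20% | FT011 30% | FT011 40% |
|---|---|---|---|
| 5% | 64% | 61% | 60% |
| 10% | 42% | 37% | 35% |
| 20% | 20% | 13% | 11% |
| 30% | 13% | 6% | 3% |

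The chance that at least one of the two dose comparisons fails is 65% (rates 5/20/30%), 37% (10/30/40%), 12% (20/40/50%) and 4% (30/50/60%). With 8 evaluable per arm, one comparison fails in 72% (5 vs 20%), 46% (10 vs 30%) and 18% (20 vs 40%).

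When it can be computed, the odds ratio is still very imprecise. For 1/10 vs 4/10 it is (4/6)/(1/9) = 6.0, with Wald 95% CI 0.53 to 67.7.

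**3. Does the risk difference do better?** Take 0/10 vs 3/10, where the odds ratio is infinite. The Wilson limits are 0 to 0.278 and 0.108 to 0.603. The Newcombe limits follow:

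- lower: 0.30 − √[(0.30−0.108)² + (0.278−0)²] = −0.038
- upper: 0.30 + √[(0.603−0.30)² + 0²] = 0.603

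The result is 30 points (−3.8 to 60.3), which is wide but exists. For 0/10 vs 5/10 it is 50 points (11.7 to 76.3).

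**4. Which estimate suits the CRISS score?** The score lies between 0 and 1, some participants are assigned 0, and no change on any component gives logistic(−5.54) = 0.004. Values will therefore tend to cluster near zero. A constructed example:

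- placebo: five at 0.004, then 0.01, 0.02, 0.05, 0.1, 0.3
- FT011: 0.004, 0.004, 0.01, 0.02, 0.05, 0.1, 0.7, 0.8, 0.9, 0.95

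Responders are 0/10 vs 4/10, a difference of 40 points. The Hodges-Lehmann shift (median of the 100 pairwise differences) is only 0.046. The probability that an FT011 participant scores higher, counting ties as half, is (2.5 + 2.5 + 5.5 + 6.5 + 7.5 + 8.5 + 4 × 10)/100 = 0.73. The shift understates the contrast and the probability does not.

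**The case against.** The strongest reply is that much of the information is already planned. Counts and percentages per arm allow a raw risk difference to be read off. The protocol synopsis promises descriptive statistics for all efficacy endpoints, and the SAP summarises SCTC-DI by arm. All five CRISS components get differences with intervals. SAP section 6.1 allows 95% CIs where appropriate, and section 8 leaves table content to templates that are not in the documents. The comparisons are optional and exploratory, on secondary endpoints of a trial whose primary objective is pharmacokinetic.

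This rules out several stronger readings:

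- *No usable effect size will result.* Not supported, because raw differences can be derived. Only a pre-specified contrast with an interval is missing.
- *The odds ratio will usually fail.* This depends on an unstated placebo rate. It is not true at 30% with FT011 at 30-40%.
- *The CRISS equation implies low response rates.* If only mRSS changes, it must fall by (5.54 + ln 1.5)/0.81 = 7.3 points to reach 0.60. That holds the other four components at zero. Take mRSS −4, FVC +3, HAQ-DI −0.25, patient global improved by 10 mm and physician global by 20 mm. The linear score is −5.54 + 3.24 + 0.63 + 0.85 + 0.40 + 0.88 = 0.46, giving 0.61, a responder. Placebo participants also stay on standard-of-care medication.
- *The Wilcoxon p-values will be non-significant whatever the effect.* Simulated power of the exact test at 10 vs 10, assuming a normal shift, is 10%, 32% and 67% when the probability of superiority is 0.6, 0.7 and 0.8.
- *The CMH test is unsound.* Its maximum size at 10 vs 10 is 4.2%.

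What the reply does not answer is that the general clause on intervals names neither a measure nor a method for these outcomes. That choice would then be open after unblinding.

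**Conclusion.** The point holds as a reporting gap. In the SAP text, the CRISS score, CRISS response and SCTC-DI have tests and descriptive output but no between-arm estimate with an interval, while five other efficacy endpoints have one. The single effect measure for CRISS response stands only in the protocol, and its absence from the SAP is unexplained. Its fragility ranges from serious (a failure chance of 35% or more at placebo rates of 10% or below, with FT011 at 20-40%) to minor (3-6% at 30%, with FT011 at 30-40%). The range rests on assumed rates and on 10 evaluable participants per arm. The primary pharmacokinetic objective is not affected, and the planned tests can stay.

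**What to change.** In SAP section 14.2.1.10:

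- **CRISS response:** report the risk difference for each dose versus placebo, with a Newcombe or Miettinen-Nurminen 95% CI, in place of or ahead of the odds ratio. If the odds ratio is dropped, list this in SAP section 3.3. Restrict the CMH code to one dose and placebo at a time, as the protocol describes.
- **CRISS and SCTC-DI scores:** beside each Wilcoxon p-value, report the probability that an FT011 participant does better than a placebo participant, counting ties as half, with a 95% CI. Name the interval method in advance and state the direction (higher CRISS is better, lower SCTC-DI is better).
- **Hodges-Lehmann shift:** do not rely on it for the CRISS score, for the reason shown in the worked example.

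The cost is some programming and a few table columns, with no new data, visits or participants. The intervals will be wide, which is a fair picture of what 10 per arm can show.
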